7.1.4. Per-Protocol Population (PP)

Includes all subjects who complete study treatment and have no significant protocol deviations. Subjects who are members of the PP population will be analyzed as randomized. This will be a secondary supporting population for the co-primary efficacy analyses.

7.1.5. Safety Population (SP)

Includes all subjects who receive at least one dose of double-blind study treatment and have at least one post-dose visit. Subjects who are members of the safety population will be analyzed according to the treatment received. This population will be used for all safety analyses.

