9.7.3 Reporting Adverse Events

Adverse events that occur from the time of informed consent through completion of the last study visit should be reported. Any AE that the Investigator becomes aware of that occurs within 30 days of study completion or withdrawal should also be reported.

Any SAEs occurring in a subject receiving study medication must be reported to the Sponsor within 24 hours of the site being informed of the event, even if the event does not appear to be drug-related. This reporting must be done by faxing the appropriate completed form (SAE form or Exposure during Pregnancy form) to the Sponsor. Any pertinent follow-up information should be provided in a similar manner. Contact information is provided below:

[REDACTED]

[REDACTED]

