11.5 Safety Endpoints

Safety endpoints will be reported on the Safety population. Subjects will be reported according to the treatment they actually received. Safety assessment will be based on descriptive statistics and individual subject listings. No statistical tests will be performed for any of the safety assessments.

All reported AEs will be mapped to the Medical Dictionary for Regulatory Activities (MedDRA) system organ classifications (SOCs) and preferred terms (PTs). If a subject reports multiple events of a single PT, the greatest severity and strongest investigator assessment of relationship to study treatment will be assigned to that PT. Summaries of TEAEs will include any AEs reported beginning with the first dose of study treatment on Day 1. The occurrence of TEAEs will be summarized by treatment group using SOCs, PTs, and severity. Separate summaries of treatment-emergent SAEs, TEAEs considered related to study treatment, and events leading to the discontinuation of study drug will be generated.

Descriptive summaries of vital signs, clinical laboratory results, USP results, and the C-SSRS results will be presented by study visit and treatment group. The number and percentage of subjects with treatment-emergent clinical laboratory abnormalities will be summarized by treatment group. Normal range clinical laboratory shifts from baseline to end of study will be summarized by treatment group.

Concomitant medications will be coded using the World Health Organization (WHO) dictionary. These data will be summarized by treatment group. Previous and concomitant medications will be presented in a data listing.

Subject disposition will be presented for all subjects. The numbers of subjects who complete the study and who discontinue early from the study will be provided. The reasons for early discontinuation will also be presented.

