10. SAFETY ANALYSES

All Safety analyses will be conducted using the Safety population. All safety analyses will be completed using the actual treatment a subject received (i.e. “as Treated”).

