10.1. Adverse Events

The number and percent of subjects with any treatment-emergent adverse events (TEAEs) will be displayed by system organ class and preferred term (MedDRA Version 18.0) for each treatment group. Within each preferred term, subjects will be counted only once if they had more than one event reported during the treatment period.

TEAEs will also be summarized by greatest reported severity for each event preferred term. Counts indicate subjects reporting one or more TEAEs that map to the severity grade classification for each preferred term. At each level of summarization (system organ class or event preferred term) subjects are only counted once and the worst severity case of repeated instances of the same TEAE will be used in tabulations. TEAEs will also be summarized by strongest investigator assessment of relationship to study drug in a similar manner.

Analyses of AEs will be performed for those events that are considered treatment emergent, where treatment emergent is defined as any AE with onset or worsening on or after the first dose of study drug up until 30 days after the last dose of study drug.

Treatment emergent summarization will be characterized by serious or not, the severity and the relationship with the study drug. A conservative approach will be taken to assess the relationship of an AE to study drug; if the relationship of an event is missing, it will be considered treatment-related. Missing severity will be coded as severe.

All TEAEs will be listed individually by subject. In addition, a separate listing will be produced for AEs that are not treatment-emergent.

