10.2.3. Adverse Events Leading to Discontinuation of Study Drug

The number and percent of subjects with TEAE's leading to discontinuation, or interruption, of study drug will be displayed by system organ class and preferred term for each treatment group. Within each preferred term, subjects will be counted only once if they had more than one TEAE leading to discontinuation, or interruption, of study drug reported during the treatment period.

A listing will be produced for all subjects who reported serious TEAEs or who discontinued study drug due to TEAEs.

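### The Safety population requires a post-dose visit, so a known adverse event in a dosed subject who never returns drops out of every safety table

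*SAP*

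**What the plan says.** SAP 7.1.5 sets two conditions for the Safety population: "Includes all subjects who receive at least one dose of double-blind study treatment and have at least one post-dose visit". Protocol 11.2 sets the same two, so the documents agree. SAP 10 then states: "All Safety analyses will be conducted using the Safety population". Protocol 11.5 likewise confines safety reporting to this population.

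The rules for collecting and classifying adverse events do not depend on a visit:

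- Protocol 9.7.3: "Any AE that the Investigator becomes aware of that occurs within 30 days of study completion or withdrawal should also be reported". The same section starts the 24-hour clock for serious events when the site is informed.
- SAP 10.1, on treatment emergence: "where treatment emergent is defined as any AE with onset or worsening on or after the first dose of study drug", up to 30 days after the last dose.
- Protocol 11.5: "Summaries of TEAEs will include any AEs reported beginning with the first dose of study treatment on Day 1".

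On timing, Protocol 6.2 has the site give the first dose at Visit 2 (Day 1), and Protocol 6.3 puts the next scheduled visit at Day 10 (±3 days). Neither document defines a post-dose visit.

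**The concern.** A safety population should hold everyone exposed to study drug. Here a second condition is added that can only be met after randomisation and after exposure. Whether a subject comes back can depend on how the drug was tolerated, and the interval with no scheduled visit is the 9-day titration towards two different doses or placebo. The exclusion could therefore fall unevenly across 80 mg, 40 mg and placebo.

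At stake are the arm-level rates of treatment-emergent events, serious treatment-emergent events and events leading to discontinuation. Safety is part of the primary objective (Protocol 3.1) and is assessed descriptively: "No statistical tests will be performed for any of the safety assessments". The tabulated rates, together with the listings, are therefore the safety result, and there is no further analysis that would correct them.

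**Working it through.** **Can the situation arise under the text?**

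1. The subject takes the first dose at the site at Visit 2 (Protocol 6.2). The first condition is met.
2. The subject stops before Visit 3 and attends nothing afterwards. Protocol 12.4 lists loss to follow-up and withdrawal of consent among the reasons for leaving. It asks for the Visit 6 assessments after early discontinuation on a best-effort basis, so that visit is not guaranteed. The second condition fails.
3. An event still reaches the site, for example through a telephone call or a hospital report. Protocol 9.7.3 requires it to be reported.
4. Its onset is after the first dose, so it is treatment-emergent under SAP 10.1.
5. The subject is outside the Safety population, so SAP 10 leaves both subject and event out of the tables. Nothing elsewhere in either document brings them back in.

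**How large is the effect?** The documents give no count of dosed non-returners and no figure that depends on one, so there is nothing to reproduce. What follows is illustration. N = 170 per arm is the planned size (Protocol 5); everything else is assumed.

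Let E of N dosed subjects have the event, and let k be excluded, of whom a have the event.

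- Rate among all dosed: E/N
- Rate shown in the table: (E − a)/(N − k)
- The shown rate is too low when N(E − a) < E(N − k), that is, when a/k > E/N. It is too high when a/k < E/N.

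Take E = 10 discontinuations for adverse events, so E/N = 10/170 = 5.88%.

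| Excluded (k) | With event (a) | Rate shown | Change (points) |
|---|---|---|---|
| 1 | 1 | 9/169 = 5.33% | −0.56 |
| 3 | 3 | 7/167 = 4.19% | −1.69 |
| 5 | 0 | 10/165 = 6.06% | +0.18 |

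A commoner event gives a similar picture. If 2 subjects in an arm are excluded and one of them had the event, the table shows 17/168 = 10.1% against 18/170 = 10.6% for all dosed.

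One subject is 1/170 = 0.59% of a planned arm.

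**The case against.** The strongest reply is that the harm needs four things together: a dose, no later visit of any kind, an adverse event, and news of that event reaching the site. Subjects who are lost or withdraw consent are those least likely to have an event reported, so they mostly affect the denominator. The protocol also pulls known events towards a visit: Visit 6 procedures are meant for all early withdrawals (6.5), a suspected event triggers evaluation (9.7.1), subjects withdrawn after stopping drug are followed for safety (7.1.1), and clinically significant events stay under medical supervision (9.7.4). If an unscheduled visit counts as a post-dose visit, the gap shrinks further. All of this stands. It makes the case uncommon, and it makes the three-subject row above unlikely.

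The information is also not lost altogether. SAP 10.1 says: "All TEAEs will be listed individually by subject". SAP 10.2.3 adds: "A listing will be produced for all subjects who reported serious TEAEs or who discontinued study drug due to TEAEs". SAP 10.2.1 and 10.2.2 provide narratives for deaths and serious treatment-emergent events, and SAP 10.6 allows extra safety analyses without amending the SAP. This stands too, but listings and narratives do not correct arm-level rates, and an all-dosed table added under SAP 10.6 would be post hoc. The disposition table in SAP 8.1 gives randomised and Safety counts, but it does not separate dosed non-returners from subjects never dosed.

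Two supporting arguments should not be leaned on. Protocol 11.5 opens by limiting reporting to the Safety population, so its sentence on events from the first dose can be read as setting a start time within that population; it is not a clear contradiction. And the aim of improved tolerability in Protocol 2.1 is set against baclofen, which is not an arm of this trial.

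**Conclusion.** The concern holds. As written, a treatment-emergent event known to the site is left out of every safety table when the dosed subject has no later visit. This follows from the definitions alone, taking post-dose visit in its ordinary sense of Visit 3 or later, or an early-termination visit.

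The numerical effect is probably small and cannot be derived from the documents. Under the assumed inputs, one lost subject with the event moves a 5.9% rate by about 0.6 points. The direction is uncertain, because the shown rate falls only if non-returners have the event more often than the arm as a whole. No hypothesis test or success criterion is affected. This should be changed because the selection is avoidable and the correction is cheap, not because the trial's conclusions are in danger.

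**What to change.** Before unblinding, delete the post-dose-visit condition from Protocol 11.2 and SAP 7.1.5. The Safety population then consists of every subject who took any double-blind study drug, analysed by treatment received.

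The change is one clause in two documents and needs no new data. The protocol part needs an amendment with Sponsor and IRB/IEC review and approval (Protocol 12.2). The statistical cost is that a few subjects with little or no follow-up enter the denominators and count as event-free if their events were never recorded, which slightly lowers the rates. That is a smaller fault than leaving out known events in exposed subjects. Summaries by visit report the number of non-missing values (SAP 7.4.1), so subjects without post-dose measurements do not distort them.

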7.2. Covariates and Subgroups

7.2.1. Planned Covariates

The efficacy analyses will include study center as an effect and baseline values (where applicable) as a covariate. Other covariates may be used for exploratory analyses.

7.2.2. Planned Subgroups

The co-primary efficacy endpoints will be summarized with descriptive statistics for the following subgroups: study center, duration of MS, presence or absence of disease modifying agents, class of anti-spasticity agent, prior baclofen use, baseline EDSS score, and age.

7.3. Management of Analysis Data

7.3.1. Data Handling

Unscheduled or repeated laboratory results will not be analyzed for the summary of continuous values but will be included in the laboratory shift tables as follows. Unscheduled tests will be included with the time of the nearest regularly scheduled test. If there is a scheduled test and one or more unscheduled tests assigned to the same time point, the most conservative test (i.e., a test with low or high results) will be used. Repeated tests will be included only if they reflect abnormal (low or high) results and the corresponding original results are normal. All laboratory values, for all visits, will be provided in by subject listings.

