6.2 Visit 2 (Baseline) – Day 1 (±3 days)

This visit takes place after the subject has completed withdrawal of all anti-spasticity medications. Assessments/procedures will include the following:

- Review eligibility according to the inclusion ([Section 5.1](#)) and exclusion criteria ([Section 5.2](#)).
- Review study discontinuation criteria ([Section 12.4](#)).
- Verify complete washout and abstinence from oral anti-spasticity medications for at least the past 14 days ([Section 7.7](#)).
- If the subject is eligible for randomization, obtain a randomization code and medication kit number for that subject ([Section 7.4](#)).
- The study evaluator will perform the TNmAS-MAL ([Section 8.1](#)).
- Record vital sign measurements, including BP, heart rate, respiratory rate, and body temperature ([Section 9.2](#)).
- Collect blood and urine samples for hematology, serum chemistry, and urinalysis ([Section 9.5](#)). Subject should be fasting if possible. As per Exclusion Criterion 12, if, in the opinion of the investigator, a subject has clinically significant abnormal laboratory value(s) at Visit 2 (Baseline), they will be excluded from the study.
- Collect a urine sample for pregnancy testing for women of childbearing potential ([Section 7.8](#)).
- Dispense the study medication. The Investigator will explain to the subject how to take the study medication and the regimen to be followed until the next visit ([Section 7.5](#)).
- The site will administer the first daily dose of study medication to the subject.
- Administer the C-SSRS ([Section 9.6.3](#)).
- Administer the EDSS ([Section 8.4](#)).
- Administer the USP questionnaire ([Section 9.6.2](#)).
- Record any adverse events (AEs) that have occurred ([Section 9.7](#)).

- Record all concomitant medications/therapies the subject is currently taking ([Section 7.7](#)).
- Schedule the next study visit.

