10.3. Clinical Laboratory Evaluations

Clinical Laboratory results will be summarized descriptively for each treatment group by time point for the observed value as well as for the change from baseline value. In addition, laboratory shift tables will be provided for all laboratory parameters where low/normal/high or abnormal/normal status can be ascertained. Listings of individual laboratory parameters by visit with normal ranges and abnormality assessments will also be completed by subject.

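### As written, SAP 7.3.1 can place an on-drug unscheduled laboratory result at baseline and so remove a normal-to-abnormal shift from the shift tables

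*SAP*

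**What the plan says.** SAP 7.3.1 keeps unscheduled and repeated laboratory results out of the continuous summaries but admits them to the shift tables under three rules:

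- **Placement of unscheduled tests:** "Unscheduled tests will be included with the time of the nearest regularly scheduled test".
- **Choice within a time point:** where a scheduled test and one or more unscheduled tests share a time point, "the most conservative test (i.e., a test with low or high results) will be used".
- **Repeats:** "Repeated tests will be included only if they reflect abnormal (low or high) results and the corresponding original results are normal".

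SAP 10.3 then plans that "laboratory shift tables will be provided for all laboratory parameters where low/normal/high or abnormal/normal status can be ascertained". Protocol 11.5 plans shifts from baseline to the end of the study by treatment group, and separately that "The number and percentage of subjects with treatment-emergent clinical laboratory abnormalities will be summarized by treatment group".

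On timing, protocol 6.2 makes Visit 2 (Baseline, Day 1) a scheduled laboratory visit and adds: "The site will administer the first daily dose of study medication to the subject". The next scheduled laboratory visit is Visit 3, Day 10 (±3 days), in protocol 6.3.

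Neither document defines laboratory baseline as the last value before dosing. SAP 7.4.1 uses a baseline value in the change score without defining it. The rule in SAP 10.1 that turns on the first dose applies to adverse events only.

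**The concern.** Choosing the abnormal result is conservative after baseline, because it makes a new abnormality easier to see. At baseline an on-drug abnormal result has the opposite effect: it makes the subject look abnormal before treatment and hides a later abnormality in the same direction.

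The placement rule looks only at distance in time. It does not ask whether the test was drawn before or after the first dose. Since dosing starts at Visit 2, an unscheduled test in the following few days is on drug and falls within the 9-day titration, yet it can be closer to Visit 2 than to Visit 3.

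The by-arm shift table could then understate new abnormalities that arise early on drug. One subject could also have two baselines: the change-from-baseline summary would use the scheduled Visit 2 value, because unscheduled results are excluded from it, while the shift table would use the abnormal result from a few days later. Safety is part of the primary objective and the laboratory analysis is descriptive, so the summary tables should be right.

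**Working it through.** The plan states no figure on this point, so there is nothing to reproduce. The check applies the SAP 7.3.1 wording to the visit schedule.

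**Inputs**
- Visit 2 and first dose: Day 1 (protocol 6.2).
- Visit 3: Day 10, window Day 7 to Day 13 (protocol 6.3).
- Placement and choice rules: SAP 7.3.1.

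**Step 1: which on-drug days go to baseline.** A test on day d goes to Visit 2 if d − 1 < V3 − d, that is, if d < (1 + V3)/2.

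| Visit 3 on | Midpoint | Days placed at baseline | Tie |
|---|---|---|---|
| Day 7 | (1 + 7)/2 = 4 | 2 to 3 | Day 4 |
| Day 10 | (1 + 10)/2 = 5.5 | 2 to 5 | none |
| Day 13 | (1 + 13)/2 = 7 | 2 to 6 | Day 7 |

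The SAP gives no rule for a tie.

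**Step 2: what the shift table shows.** Take an analyte that is normal (N) at Visit 2 and high (H) on an unscheduled Day 4 test, with Visit 3 on Day 10. As written, Day 4 goes to baseline and H replaces N there. Under a pre-dose baseline, Day 4 goes to Visit 3.

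| Later scheduled results | As written: Visit 3, Visit 5 | Pre-dose baseline: Visit 3, Visit 5 |
|---|---|---|
| High at both | H→H, H→H | N→H, N→H |
| Normal at both | H→N, H→N | N→H, N→N |
| Normal at Visit 3, high at Visit 5 | H→N, H→H | N→H, N→H |

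In all three patterns the normal-to-high shift disappears as written. Where the value resolves, the subject appears to have improved on treatment. The loss applies to a later abnormality in the same direction; an analyte high at the misplaced baseline and low later would still show a shift.

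**Step 3: does another section prevent this?** SAP 10.3 gives no baseline rule for the shift tables, SAP 7.4.1 does not define baseline, and SAP 10.1 covers adverse events only. None of them closes the gap.

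**The case against.** The strongest reply is that the SAP never says that an on-drug result is baseline. Protocol 4.1 describes the Visit 2 evaluation as confirming eligibility before randomization, and SAP 7.4.1 separates post-baseline measurements from the baseline value. A careful programmer might therefore keep post-dose results out of baseline. It is fair that the rule reaches baseline through the lack of an exception and not by an express statement. But the placement rule is stated without limit, and a prespecified plan should not depend on a programmer adding one.

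Several limits on the consequences stand:

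- **Other outputs.** A reader might infer that the shift tables are the only place where these results appear. They are not: SAP 7.3.1 and 10.3 list every value by subject, the latter with normal ranges and abnormality assessments. Listings do not, however, correct a by-arm table.
- **Adverse events.** Under protocol 9.5 a clinically significant abnormality that needs treatment or leads to discontinuation is recorded as an adverse event. Its treatment-emergent status under SAP 10.1 depends on onset relative to the first dose, so the laboratory rule does not touch it.
- **The treatment-emergent count.** Protocol 11.5 lists it apart from the shift summary, and neither document says how it is built. It is affected only if it is derived from the same categories.
- **Repeats.** A reader might infer that repeats cause the same problem. The wording allows it, but protocol 9.5 asks for repeats of abnormal values, and SAP 7.3.1 ignores a repeat when the first result was already abnormal. This route should be uncommon, and the point does not rest on it.
- **Pre-dose results.** One might also argue that taking the worst of several pre-dose results is wrong. That is debatable: such an abnormality did exist before treatment, and recording it at baseline is defensible.

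**Conclusion.** The point holds, within limits. Followed literally, SAP 7.3.1 places unscheduled on-drug tests from Days 2 to 5 at baseline when Visit 3 is on Day 10, and from Days 2–3 up to Days 2–6 across the Visit 3 window. A new abnormality found on such a test is then tabulated as abnormal-to-abnormal or abnormal-to-normal. This rests on two assumptions: that Day 1 is the day of the first dose, as the visit schedule has it, and that the rule is programmed as written.

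The effect is confined to the descriptive shift tables and any treatment-emergent laboratory count derived from them. The scheduled continuous summaries, the listings, adverse event reporting and the efficacy analyses are unaffected.

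The number of subjects cannot be estimated, because the documents give no rate of unscheduled draws. A reader might assume that 1 to 5% of the 510 subjects have a draw in the window, which gives 510 × 0.01 ≈ 5 to 510 × 0.05 ≈ 26. That range has no basis in the documents and counts draws, not errors: misclassification also needs a normal Visit 2 result and an abnormal result on the draw. Nor do the documents show that early draws would be more frequent on AERT. That two-thirds of subjects are on AERT is only the 1:1:1 allocation and is not evidence of a differential effect.

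**What to change.** In SAP 7.3.1:

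1. Define laboratory baseline as the last non-missing result before the first dose.
2. Assign tests drawn after the first dose only to post-baseline visits, the first being Visit 3.
3. Apply the most-conservative-result rule only to post-baseline time points.

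It would help to settle two details in the same edit: a tie rule for a test equidistant from two visits, and a convention for a Day 1 sample with no recorded collection time. SAP 10.3 should also say whether the treatment-emergent count in protocol 11.5 uses this baseline.

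The cost is a few sentences and one programming condition before unblinding. No new data are needed, and no efficacy analysis changes.
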